Sample size and power analysis. The sample N of 160 was set primarily for practical and clinical reasons and not driven by estimated effect sizes or hypothesis testing. We expect to have representation (although not equal) among males and females, and across ethnic groups consistent with our current trial of TSP. We also expect to have representation across levels of smoking and drinking, and readiness to quit using both substances. We anticipate an attrition rate of 30% at 3, 6, and 12 months, yielding a final sample size of 112 (56 in each group), enabling us to compare groups on primary and secondary outcomes at each timepoint. This will also generate an effect size estimate that will be useful for powering a larger trial.

A goal of 6 participants will be recruited per week during the 6-month recruitment period, which is in line with recruitment for our feasibility trial and current RCT.¹¹¹

Procedures. Participants will be recruited through Facebook and Craigslist advertisements, using a similar strategy to that of focus group and usability-testing. All advertisements will provide a link to the study’s website, with eligibility questions. If respondents are eligible, then they will be taken to the informed consent webpage. Participants consenting to participate in the study will be asked to verify age by sending proof through email or social media, a process used successfully in [name] previous research. Verified participants will be emailed a baseline assessment. Those completing the baseline assessment will be randomized to either TSP, or TSP+ALC, stratified based on readiness to quit smoking (Ready in the next 30 days, Not Ready in 30 days) and smoking pattern (daily vs. non-daily), variables known to be related to outcomes and addressed by the intervention.¹⁶¹ A stratified random assignment program will be developed in consultation with [name], and used currently in [name] RCT of TSP. All participants will then be assigned to a secret group tailored to their condition and readiness to quit tobacco. Groups will begin when there are approximately 12 participants enrolled, as that has been deemed the optimal number based on analyses of engagement in our previous work.^{109, 162} Groups will receive one social media post daily for 90 days and weekly “The [name] In” counseling sessions managed

[figure not shown]

Figure 2. Participant flow through the study

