Feasibility analyses will examine four areas: **(1) Recruitment Efforts:** We will evaluate (a) length of time to recruit N=160 participants to enroll in the pilot trial, and (b) demographic, smoking, and drinking characteristics of those eligible and who enroll; **(2) Usability:** We will calculate mean responses to Likert scale items of the usability measure and any sections with lower than median values will indicate changes should be made before future investigations take place. **(3) Implementation of biochemical verification of tobacco abstinence:** We will determine the proportion of participants in each condition reporting 7-day point prevalence abstinence at 3-month follow-up that completes a saliva cotinine test and the rate of discordance between saliva cotinine results and self-report. **(4) Attrition:** We will track the number and proportion of participants that completes each follow-up assessments and compare these numbers to previous Internet cessation trials (attrition as high as 75%^{52, 53, 199-201}).

Analyses for Specific Aim 2: Preliminary efficacy.

Descriptive statistics will summarize sample characteristics and the extent of intervention delivery in each group. We will examine treatment condition and baseline descriptive characteristics as predictors of

attrition at trial end (month 3) and propose to control for predictors of attrition as covariates in model testing. Missing data will be minimized through online assessment. When subjects do not complete online assessments, they will be re-contacted through Facebook or email to obtain missing information. For each test related to smoking, two sets of outcome analyses will be conducted - one with all participants who are maintained in the study, and another based only on biochemically verified smoking abstinence rates to allow for direct comparison of findings with the research literature.

Primary outcome: To test for the effects of treatment condition on smoking abstinence at 3- through 12-months, we will estimate and test a mixed-effects logistic regression model. Abstinence status will be examined as 7-day point prevalence. The independent variables are TSP versus TSP+ALC plus variables that are related to abstinence such as cigarettes per day, differ by condition at baseline or predict attrition. We will use multiple imputation procedures to impute missing data.

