Secondary outcomes: For secondary outcomes we will estimate and test mixed effects logistic and multinomial regression models for longitudinal ordinal response data to model secondary outcomes for tobacco use and alcohol use across time (3, 6, 12 months): 1) reduction of cigarettes by 50% or more (y/n), 2) tobacco or alcohol quit attempt (y/n; 2 models), 3) readiness to quit tobacco and alcohol (Precontemplation, Contemplation, Preparation, Action/Maintenance; 2 models); and 4) commitment to abstinence (no goal, intermediary goal, complete abstinence). In parallel, mixed effects linear regression models will model the following continuous outcomes over time: 1) past 30 day HED; 2) average number of drinks per week in the past 30 days, 3) severity of alcohol use (AUDIT-C score); 4) desire to cut down tobacco and alcohol use (1 to 10; 2 models); and 5) sum of days using either tobacco or alcohol in the past 30 days. Independent variables in all models will be treatment condition, abstinence status, and covariates identified as relevant to smoking characteristics in the literature.

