Analyses for Specific Aim 3 (Engagement and Patterns of Social Interaction). Analyses will use Facebook data extracted from the private groups we develop on Facebook using the Facebook API. All data will be de-identified and transferred to **[name]**, expert on social media analytics at Drexel University, for analysis. The data will include the content of the posts and comments, the activity of each participant (e.g., number, content, and time of all comments), and interactions among participants. We will determine patterns of engagement, type of posts that are most “engaging” to participants, and relate engagement to smoking and drinking outcomes using three main analyses: **(1) Patterns of engagement:** Total number of “likes” and comments to Facebook groups over the 3 month intervention period will be tallied for each group (TSP, TSP+ALC), and the non-parametric Kruskal-Wallis ANOVA will compare likes and comments in each intervention and include covariates of baseline characteristics (readiness to quit tobacco/alcohol, daily/non-daily smoking status, gender) and group membership; a social network analysis will examine the interaction patterns among different types of users with which participants engage in each intervention; a content analysis will evaluate the content of comments within each group and observe differences among the two groups; **(2) Success of specific posts:** To evaluate which posts are most successful at engaging participants, Drs. [name] and [name] will collaborate on coding posts based on content type (e.g., alcohol/tobacco, Motivational Interviewing, specific CBT skills). Specific codes will be determined upon design of the TSP+ALC intervention). ANOVA will then be used to examine likes and comments by post type within each group (TSP, TSP+ALC) **(3) Engagement and outcomes:** We will compare TSP and TSP+ALC groups on the relationship between intervention engagement (FB comments) and primary tobacco and alcohol outcomes (abstinence, heavy drinking days) at the end of the 3 month intervention period. Logistic regression will be used to analyze tobacco abstinence, and linear regression for days of heavy drinking at 3 months, controlling for any baseline differences in treatment groups. Kruskal-Wallis tests will evaluate the effect of incentive condition (personal, altruistic, no incentive) on comments to the Facebook group, in both the full sample and only those who made at least one comment to the group to address likely skewed data.

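### The efficacy models are not required to contain the two factors used to stratify randomisation; naming them as fixed covariates is a cheap improvement with a modest gain

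*Combined protocol and SAP*

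**What the plan says.** Section C.8 (Efficacy Trial, Procedures) randomises participants "stratified based on readiness to quit smoking (Ready in the next 30 days, Not Ready in 30 days) and smoking pattern (daily vs. non-daily") and justifies the choice by describing these as "variables known to be related to outcomes and addressed by the intervention".

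Section C.9 (Preliminary efficacy, Primary outcome) states that "we will estimate and test a mixed-effects logistic regression model" for abstinence from 3 through 12 months. The independent variables are treatment condition "plus variables that are related to abstinence such as cigarettes per day, differ by condition at baseline or predict attrition". Cigarettes per day is the only covariate named.

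Section C.9 (Secondary outcomes) covers tobacco and alcohol outcomes alike. Besides treatment and abstinence status, its models take "covariates identified as relevant to smoking characteristics in the literature". No covariate is named.

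Both stratification factors are named in one analysis only, the Aim 3 comparison of likes and comments, which will "include covariates of baseline characteristics (readiness to quit tobacco/alcohol, daily/non-daily smoking status, gender) and group membership".

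On size, section C.8 says: "The sample N of 160 was set primarily for practical and clinical reasons and not driven by estimated effect sizes or hypothesis testing". It also says that the trial should supply an effect size for powering a larger one.

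**The concern.** An analysis normally conditions on the factors that restricted the randomisation. Here the design uses two factors because they are prognostic, and the efficacy models then leave their entry to a rule that is partly data-driven and partly a matter of judgement.

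The primary rule has three routes in. The first, relation to abstinence, could admit both factors, but the plan does not say whether the relation is to be known beforehand or observed in the trial data. The second, difference by condition at baseline, is a poor reason for adjustment in any randomised trial, and stratification makes these factors the least likely to meet it. The third, prediction of attrition, depends on the data. Two analysts could follow the rule and fit different primary models. The secondary rule is looser still: it draws covariates for drinking outcomes from what is relevant to smoking.

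The main stake is the estimate. In logistic regression the treatment odds ratio depends on which prognostic covariates are in the model, so the effect size handed to the larger trial would depend on a choice not fixed in advance. Some loss of power is a lesser stake, since the sample size was not set by power.

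**Working it through.** **The plan's own figure.** 160 × (1 − 0.30) = 112, or 56 per group, as section C.8 states. No alpha, effect size or power is given, so there is no power figure to reproduce.

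**Inputs from the documents.** n = 112; 19% ready to quit (current TSP trial, preliminary studies); 88% daily smokers (same trial, NRT section); base abstinence 7% (7.1% verified at 3 months, current trial) or 21% (self-reported at 6 months, feasibility trial).

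**Assumptions not in the documents.** Two-sided alpha 0.05; permuted blocks of 4 within the four strata; treatment OR 1 or 3; stratum ORs as listed (ready / non-daily).

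**Binary outcome.** Single-timepoint logistic model, likelihood-ratio test, 3,000 simulated trials per row. Both models were fitted to the same trials: treatment only, and treatment plus both factors.

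| Base rate | Stratum ORs | Power without | Power with | Null rejection without / with |
|---|---|---|---|---|
| 7% | 1.5 / 1.5 | 47.1% | 47.9% | 7.9% / 8.1% |
| 7% | 2 / 2 | 46.3% | 47.7% | 6.8% / 6.8% |
| 7% | 4 / 2 | 41.7% | 44.6% | 6.4% / 6.9% |
| 7% | 6 / 4 | 35.9% | 41.8% | 6.4% / 7.7% |
| 21% | 1.5 / 1.5 | 74.3% | 75.3% | 5.7% / 5.9% |
| 21% | 2 / 2 | 75.4% | 76.6% | 5.0% / 5.8% |
| 21% | 4 / 2 | 70.0% | 73.8% | 5.1% / 6.1% |
| 21% | 6 / 4 | 63.8% | 70.9% | 3.9% / 5.6% |

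In no row does omission raise the false-positive rate. At the 7% base rate both tests run above 5% because events are few. Part of each power gain reflects the adjusted test rejecting slightly more often overall.

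**Where the binary loss comes from.** At 21% with ORs 4 / 2, the mean model standard error is 0.434 without the factors and 0.468 with them, so omission makes it smaller. What changes is the estimate: mean log OR 1.036 versus 1.164, that is OR e^1.036 = 2.8 versus e^1.164 = 3.2. The simulated treated-arm rate is 0.422, so the true marginal log OR is ln(0.422/0.578) − ln(0.21/0.79) = 1.010, against a conditional value of ln 3 = 1.099. Of the 0.128 gap, 0.089 is therefore the difference between marginal and conditional odds ratios; the rest is small-sample bias, which is larger in the adjusted model.

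**Continuous outcome.** If readiness explains a share R² of variance and allocation is balanced within strata, the unadjusted model's standard error is too wide by a factor 1/√(1 − R²). In the normal approximation its true size is 2[1 − Φ(1.96/√(1 − R²))]:

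- R² = 0.10: 1.96/0.949 = 2.07, size 3.9%.
- R² = 0.20: 1.96/0.894 = 2.19, size 2.8%.

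A simulation (10,000 runs, n = 112) gave 4.2% and 3.0%. Power rose from 78% to 81% and from 78% to 85% on inclusion. At R² of 2% to 5% the gain was 1 to 2 points. All R² values are assumed.

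**Sparse data.** 112 × 0.071 ≈ 8 verified abstainers per timepoint. Non-daily smokers: 112 × 0.12 ≈ 13. If they abstain at the same rate, the chance of no event among them is 0.929^13 = 38%, in which case the smoking-pattern coefficient cannot be estimated by ordinary maximum likelihood at that timepoint. The ready, non-daily cell would hold about 0.19 × 0.12 × 160 ≈ 4 people at randomisation.

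**Limits.** The simulations use one timepoint and leave out repeated measures, Facebook-group clustering and imputation. In the planned mixed model, a participant-level random effect would absorb part of the omitted variation, so the shift in the odds ratio could be smaller than shown.

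**The case against.** The strongest reply is that the primary rule already lets the factors in: it admits variables related to abstinence, and section C.8 has classified both factors as related to outcomes. The measures section adds that stage of change predicts quitting. On that reading the gap is an unnamed list, not an omission. This largely stands for the primary model. It does not settle the matter, because the rule never says that the design-stage judgement counts, and the secondary models use a different rule.

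A reader might infer that the plan omits the factors, that the primary model's standard errors are therefore wrong, and that power is certainly lost. The documents do not support this. Inclusion is left open rather than ruled out, and in the logistic model omission does not widen the standard error.

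A reader might also infer a large loss. Gains of 9 to 11 points (52% to 61%, 66% to 77%) appear only if abstinence is taken as 30% versus 5%, or 50% versus 10%, by readiness. Those are odds ratios of (0.30/0.70)/(0.05/0.95) = 8.1 and (0.50/0.50)/(0.10/0.90) = 9.0, for which the documents give no basis. Likewise, for readiness to explain 10% to 20% of variance with 19% ready, the groups must differ by √(0.10/(0.19 × 0.81)) = 0.81 to √(0.20/(0.19 × 0.81)) = 1.14 standard deviations. That is a lot to expect for drinking outcomes.

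Finally, this is a pilot that claims no power, so a few points change no stated decision. That stands, and it limits the weight of the point. It does not remove the dependence of the reported odds ratio on the covariate list.

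**Conclusion.** The point holds as a cheap improvement. The plan stratifies on two factors that it calls prognostic and does not ensure that any efficacy model contains them.

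If they are left out, the logistic odds ratio moves toward 1 and continuous-outcome standard errors are somewhat too wide. The test is at most mildly conservative as a result, so its validity is not threatened. The gain from inclusion is about 1 to 4 points of power for stratum odds ratios up to 4 and 2, and 6 to 7 points at 6 and 4. For continuous outcomes it is 1 to 2 points when readiness explains 2% to 5% of variance, and 3 to 7 points at 10% to 20%.

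These sizes rest on assumed prognostic strengths and on readiness and daily-smoking shares from a different trial, whose participants were not all heavy episodic drinkers. That the rule is open does not depend on them.

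**What to change.** In section C.9, state that every primary and secondary efficacy model, and the imputation model, includes readiness (ready / not ready) and smoking pattern (daily / non-daily) as recorded at randomisation, as fixed main effects, whatever their observed association with outcome. Delete difference by condition at baseline as a reason for entry. Name any further covariates in advance and keep the list short. Use no interaction between the two factors.

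State a sparse-data fallback in advance, for example penalised likelihood, or dropping smoking pattern if its coefficient cannot be estimated.

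The cost is a few sentences; both variables exist for every randomised participant. The downside is real but small: with about 8 verified abstainers per timepoint, each added term uses scarce information, and the smoking-pattern coefficient may be poorly estimated. That favours a short fixed list over the present open rule.

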While preliminary work is not necessary for a Planning Grant application (R34), our team has pilot data and expertise that is directly relevant to this application.

Development, feasibility and efficacy of the Tobacco Status Project (TSP). During her postdoctoral fellowship, [name] led a mixed-methods study to determine how young adult smokers would like to use Facebook to help change smoking behavior. About a third (31%) of survey respondents reported they would want to quit smoking using Facebook, and interest was greater among those more motivated to quit, who had made a quit attempt in the past year, and had previously used the Internet for assistance with a quit attempt (all $p<0.01$). In qualitative interviews, social support and convenience were identified as strengths of a Facebook intervention, while privacy was the main concern.⁴

[name] is currently funded with a five-year K23 career development award from NIDA to develop and test the feasibility and efficacy of Tobacco Status Project, combining Facebook contacts tailored to participants' readiness to quit smoking with a 12-week cessation program consisting of 7 state-of-the-art group cognitive-behavioral sessions occurring over Facebook text chat. A feasibility trial enrolled 79 young adults who formed 7 Facebook groups. Follow-up rates were 84% and 72% at 6 and 12 months, respectively, and reported 7-day abstinence was 21% at 6 months (9% biochemically-verified) and 18% at 12 months (9% verified).^{6,7} From baseline to 12-months, there was a significant increase in the proportion prepared to quit (13% to 46%, $p<.001$), 35% reduced their cigarette consumption by 50% or greater, and 67% reported a 24-hr quit attempt. Engagement in the intervention was high, with 92% participation in the full 3 month intervention and 61% commented on at least one post, with more commenting among those randomized to receive a personal monetary incentive.¹⁰⁹ Participants reported reading most of the Facebook posts (mean usability rating=3.3/4) and interactions from counseling sessions (3/4), thinking about what they read (3/4) and would recommend the program to others (3.3/4). Given low participation in CBT sessions (7 of 79 participated) but extremely high engagement (6/7 sessions attended on average) we incorporated the sessions directly into the Facebook groups for a larger efficacy trial currently underway.

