In a 3-year controlled trial, we are randomizing 480 young adult participants to either TSP or referral to the National Cancer Institute Smokefree.gov website (control). In 34 weeks, we have randomized 309 young adult smokers, consistent with the proposed timeline, 19% were ready to quit smoking in the next 30 days, and the TSP group has 19 groups actively running or completed. Among TSP participants in groups that have completed the 3-month intervention (n=66), 73% commented at least once to their Facebook group. At 3 month follow-up (treatment end), follow-up rate is 71%, biochemically-verified 7-day point prevalence abstinence among completed cases is 7.1% in the TSP group and 0% in the control group. A majority of participants in both groups reported a 24 hour quit attempt during the 3-month intervention period (62% TSP; 60% control). More participants in the TSP group reported intention to quit smoking in the next 30 days (43%) than those in the control group (35%). At baseline 68% of the sample drank alcohol in the past month and 51% of all drinkers reported current HED. Although promising, there is a need to determine whether expanding the intervention to address multiple substance use will yield maximal effectiveness. **This pilot work will directly inform the present study.**

Facebook Recruitment. Drs. [name] and [name]'s research has previously found social media to be an efficient and affordable source of recruitment for young adult smokers. A survey study (N=1987) reported a cost of \$4.28 per valid completed online survey, far more affordable and targeted than other online recruitment methods.¹¹⁰ The TSP feasibility trial, discussed above, reported a cost of \$8.80 per eligible consented young adult smoker into our Facebook intervention.¹¹¹ Gender and ethnicity have differed by online recruitment source in our work (e.g., Craigslist, Facebook, survey sampling), suggesting the utility of combining recruitment methods.¹¹² **Our experience with social media recruitment will inform recruitment in the present study.**

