through the study's private group pages. If participants wish to have private study interactions with study staff they can do so at any time. Three-month follow-up assessments will be emailed to participants upon completion of treatment.

Informed consent, baseline and 3, 6, and 12 month assessments will be delivered using the online survey program Qualtrics, which is HIPAA-compliant, has been used often in medical research, and is being used successfully by [name] for her current Facebook intervention study. Verification of non-smoking status will be conducted for all participants reporting no smoking in the past 7 days at the post-test assessment using mailed saliva cotinine test kits and verified online as described in the **Measures** section. Participants will receive their choice of Amazon or Best Buy gift cards in the amount of \$20 for each 20-30 minute online survey, and a bonus \$20 for completing all assessments, for a total of \$100 possible compensation for participation. Amazon and Best Buy were chosen as retail outlets given their overwhelming popularity among a large choice of retailers given in [name] previous studies with young adult smokers.^{4, 111} Assessments will not be considered complete until staff receives verification of abstinence.

Measures.

Primary outcome (tobacco):

- **Biochemically-verified 7-day point prevalence abstinence from all tobacco products** will be assessed at 3, 6, and 12 months. Participants reporting no smoking in the past 7 days will be coded as abstinent from cigarettes. Those reporting 7-day abstinence will be mailed a saliva cotinine test kit, and record two pictures: one giving a saliva sample, and another of the test result. Participants with a salivary cotinine level <11 ng/ml, indicating nonsmoking,¹⁶³ will be considered confirmed nonsmokers. Biochemical verification is recommended in randomized trials with sample sizes under 500,¹⁶⁴ saliva cotinine test kits have been successfully mailed to participants in previous studies,¹⁶⁵ and [name] is using this method successfully in her K23 Facebook smoking cessation RCT with young adults (to date, 50% reporting 7-day abstinence have successfully completed biochemical verification). If participants indicate use of an electronic nicotine delivery-system to aid in smoking cessation, saliva cotinine and reported ENDS use will be recorded and reported separately from biochemically verified abstinence.

Secondary outcomes (tobacco):

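### Multiple imputation is the only stated way to fill in missing abstinence, and no analysis tests departure from missing at random, with about 24 of 80 per arm imputed against a projected 4 to 5 verified quitters

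*Combined protocol and SAP*

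**What the plan says.** The primary outcome is biochemically verified 7-day abstinence at 3, 6 and 12 months, analysed with a mixed-effects logistic model (C.8 Measures; C.9, Primary outcome). On missing values the primary-outcome paragraph has one sentence: "We will use multiple imputation procedures to impute missing data". The imputation model, the number of imputations and any sensitivity analysis are not given.

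C.9 has other provisions that bear on missing data. Non-responders are re-contacted. Treatment condition and baseline characteristics are examined as predictors of attrition at month 3, and those predictors become covariates. Smoking outcomes are analysed twice, once in participants maintained in the study and once on verified abstinence only.

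The sample size paragraph of C.8 states: "We anticipate an attrition rate of 30% at 3, 6, and 12 months", which leaves 112 participants, 56 per arm. It also says: "The sample N of 160 was set primarily for practical and clinical reasons and not driven by estimated effect sizes or hypothesis testing". On the cotinine step, C.8 Procedures adds: "Assessments will not be considered complete until staff receives verification of abstinence".

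**The concern.** Standard multiple imputation assumes missing at random: given the variables in the imputation model, non-responders are abstinent as often as responders. In a cessation trial, people who are smoking may be less likely to answer, and baseline covariates cannot remove a dependence on smoking status at follow-up. The two sets of smoking analyses do not help. The analysis of those maintained in the study reads as a completer analysis, and the other set changes the outcome definition, not the assumption about the missing.

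The verification step may add a second mechanism in the other direction. Only people who report abstinence must return a cotinine result. If those who do not return it are treated as missing, self-reported quitters are lost while self-reported smokers are not.

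The trial is meant to produce an effect size for powering a larger trial (C.8), and a better result for TSP+ALC is the stated ground for a further application (C.11, choice of control condition). That estimate would rest on an assumption that the plan never varies.

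**Working it through.** **Inputs from the documents**
- N = 160; 30% attrition at each follow-up; 56 completers per arm (C.8, sample size). The ratio is not stated; 80 per arm is implied.
- Ongoing TSP trial at 3 months: "biochemically-verified 7-day point prevalence abstinence among completed cases is 7.1% in the TSP group and 0% in the control group" (preliminary work in section C).
- TSP feasibility trial: self-reported abstinence 21% at 6 months and 18% at 12 months; verified 9% at both.
- In the ongoing trial, 50% of those reporting abstinence had completed verification (C.8 Measures).

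**Step 1: the plan's own figure.** 160 × (1 − 0.30) = 112, or 56 per arm. It reproduces. Missing per arm and visit: 80 − 56 = 24.

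**Step 2: projected verified quitters per arm.** 56 × 0.071 = 4.0; 56 × 0.09 = 5.0. These are projections from other trials. On self-report the count would be 56 × 0.18 = 10 to 56 × 0.21 = 12.

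**Step 3: what imputation adds.** At the completer rate, 24 × 0.071 = 1.7 quitters per arm; at 9%, 24 × 0.09 = 2.2. The exact 95% interval for 4/56 is 2.0% to 17.3%, so the average number imputed could lie anywhere from 24 × 0.020 = 0.5 to 24 × 0.173 = 4.1.

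**Step 4: counting missing as smoking.** Rate among all randomised = retention × completer rate. For one arm, 0.70 × 7.1% = 5.0%; at 9% it is 6.3%.

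For the comparison, assume completer rates of 4/56 = 7.1% (TSP) and 8/56 = 14.3% (TSP+ALC). The second rate and every unequal retention below are assumptions; the plan expects 56 in each arm.

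| Retention, TSP / TSP+ALC | Rates | Difference (points) | Odds ratio |
|---|---|---|---|
| Completers only | 7.1% v 14.3% | 7.1 | 2.17 |
| 70% / 70% | 5.0% v 10.0% | 5.0 | 2.11 |
| 75% / 65% | 5.4% v 9.3% | 3.9 | 1.81 |
| 80% / 60% | 5.7% v 8.6% | 2.9 | 1.55 |
| 65% / 75% | 4.6% v 10.7% | 6.1 | 2.46 |
| 60% / 80% | 4.3% v 11.4% | 7.1 | 2.88 |

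Example, third row: 0.65 × 0.1429 − 0.75 × 0.0714 = 0.0929 − 0.0536 = 0.039; odds ratio (0.0929/0.9071)/(0.0536/0.9464) = 1.81.

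With equal attrition the absolute rates fall but the odds ratio hardly moves. With unequal attrition it moves either way. When TSP loses more people, the odds ratio rises above the completer value, and the difference exceeds the 5.0 points of the equal case, though in these rows not 7.1.

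**Step 5: unverified quitters.** If half of self-reported quitters lack a result, the number per arm is 4.0 (7.1% verified, hence 14.2% self-reported), 5.0 (18% self-reported) or 5.9 (21%). If they count as missing on top of the 24, about 28 to 30 per arm would be imputed. If they are coded not abstinent, the 24 stands. The documents do not say which applies.

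**The case against.** Several stronger readings are tempting, and the documents do not support them.

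- **That missing data get no other attention.** C.9 also plans re-contact, attrition predictors as covariates and an analysis of those maintained in the study. These are real safeguards, but none tests departure from missing at random.
- **That imputation treats dropouts as quitting like completers outright.** It does so only given the model variables, and abstinence at other visits can inform a missing one. Nor are 24 people imputed from 4: the model uses all 56 responders per arm. Few events still make it imprecise.
- **That the cotinine rule proves outcome-dependent missingness.** The sentence follows the gift-card amounts, so it may only define completion for payment. C.8 Measures confirms as nonsmokers only those below the cotinine cut-off, so an unverified quitter may simply be coded not abstinent. If such people are missing, they are self-reported quitters, and a sensitivity range covering only lower odds of abstinence would miss them.
- **That the result would change sign.** Nothing in the table does. At these completer rates, reversal under missing-as-smoking needs TSP retention more than twice TSP+ALC retention. With 30% loss in both arms, odds multiplied by 0.1 among TSP+ALC non-responders only still gives 0.70 × 14.3% + 0.30 × 1.6% = 10.5% against 7.1%. A smaller assumed effect with unequal loss could reverse (0.80 × 7.1% = 5.7% v 0.60 × 9% = 5.4%), but the documents state neither.
- **That readers would be left blind.** Attrition and, by condition, cotinine completion are to be examined, so a reader given the quitter counts could compute missing-as-smoking. A delta-adjusted result could not be recovered that way.

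It is also fair that this is a pilot not sized for testing. For 4/56 versus 8/56 the 95% half-width is about 1.96 × 5.8 = 11 points (Fisher p = 0.36), so these shifts of 2 to 4 points sit inside sampling error and overturn no significant result. That limits the weight of the point. It does not remove it, because the estimate itself is what the next trial will use.

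**Conclusion.** The concern holds in a limited form. Multiple imputation is the only stated method for filling in missing abstinence, and no planned analysis tests departure from missing at random. About 24 of 80 per arm would be imputed, against a projected 4 to 5 verified quitters per arm. The 24 follows from the plan's own attrition figure; the 4 to 5 rests on rates carried over from the earlier TSP trials.

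The main exposure is in the absolute abstinence rates (7.1% becomes 5.0% if missing means smoking), which C.9 wants to compare with the literature, and in the treatment effect if attrition differs by arm. With equal attrition the odds ratio is nearly unaffected. The coding of self-reported quitters without a cotinine result is a separate open question that could move 4 to 6 people per arm into or out of the imputed set.

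**What to change.** Keep multiple imputation as the main analysis and add to C.9:

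1. An analysis of all randomised participants with missing abstinence counted as smoking.
2. Delta-adjusted imputation, with the odds of abstinence in non-responders multiplied by a factor varied separately by arm. The range should run below 1 (for example down to 0.1), and also above 1 if self-reported quitters without a cotinine result are treated as missing.
3. A statement of whether such quitters are coded not abstinent or missing.
4. A report of where, across these analyses, the conclusion changes.

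The imputation model should be described in the same place, including whether the attrition predictors and abstinence at other visits enter it. The cost is a little more analysis work. No new data are needed.
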